1.3 DETERMINATION OF SAMPLE SIZE

No formal sample size calculation was performed for this exploratory study. It was based on medical/clinical judgment and is consistent with the sample size from similar studies in the literature (2).

Allowing for drop-out rate of 15%, a total of approximately 24 pediatric patients with moderate-to-severe AD will be enrolled to achieve 20 evaluable patients. An approximately equal number of age, gender, location of targeted lesion area and site matched healthy volunteers serving as a reference comparator cohort will be enrolled. Any drop-out healthy volunteer for whom the matched patient is considered as evaluable will not be replaced.

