1.2 STUDY DESIGN

[figure not shown]
LPS16764 is a Phase 4 open-label, exploratory study in two sites evaluating the effect of dupilumab on skin barrier function in pediatric patients aged between ≥ 6 and < 12 years old with moderate-to-severe AD. A healthy volunteer cohort will be enrolled as a reference comparator matched to AD for age-, gender-, study-site and sampling will be matched on targeted lesion area. Approximately 24 pediatric patients with moderate-to-severe AD will be enrolled to achieve 20 evaluable patients. These enrolled AD patients will receive Investigational medicinal product (IMP) dupilumab treatment during the study. Approximately 24 healthy volunteers will be enrolled to achieve 20 evaluable subjects. These enrolled healthy volunteers will not receive any IMP treatment during the study.

The maximum study duration per participant will be 32 weeks. The study will comprise of:

- Screening period 1 (Day -28 to Day -1): Participants will be evaluated according to
- Inclusion and exclusion criteria.
- Baseline visit (Week 0, Day 1): Participants who remain eligible will be enrolled.
- A 16-week treatment phase for AD patients and a 16-week observation period for healthy volunteers.
- A 12-week follow-up period.

Biomarker assessment based on lipidomics, proteomics, and transcriptomics in STS samples will be conducted at baseline (Week 0, Day 1), Week 2, Week 4, Week 8, Week 12, EoT at Week 16, and Follow-ups at Week 22 and Week 28.

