2.1.2 Missing data, outlier, and batch effect assessment

2.1.2.1 Data imputation

For each biomarker, the number of values below LLOQ will be computed by group (lesional, non-lesional and healthy skin). Values below LLOQ will be imputed according to the following rules:

- If for a given biomarker, less than 25% of all samples have values below LLOQ, all values below LLOQ will be imputed by a random number draw from a uniform distribution in $[0, \text{LLOQ}]$. The minimum computed across all samples will be used if the LLOQ is not provided.
- If more than 50% of samples have values below LLOQ, the biomarker will be discarded from statistical analyses
- If the percentage of values below LLOQ is between 25% and 50%, it will be checked if the values below LLOQ occur mostly in a specific study group. The Fisher test will be used to check the dependency between the occurrence of below LLOQ and group.
- The biomarker will be discarded from statistical analysis if the LLOQ occurrence is group independent. Values below LLOQ will be imputed by the minimum computed across all samples, otherwise.

Missing values not due to measurements being below LLOQ maybe be imputed by the mean value computed across all samples, as appropriate.

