2.5 IDENTIFICATION OF BIOMARKERS

2.5.1 Differentially expressed biomarkers

The biomarker potentially linked to the disease status (lesional, non-lesion or healthy skin) and the biomarker changing with the treatment will be identified using a linear mixed model. For each biomarker, the following model will be used to test for any interaction between group and visit for group i, visit j and subject k:

$$y_{ijk} = \mu + \text{group}_i + \text{Visit}_j + \text{group}_i \text{Visit}_{ij} + \text{Subj}_k + \varepsilon_{ijk}$$

with group, visit and interaction between group and visit considered as fixed effects and subject as random effect. Baseline will be used as reference visit and healthy skin as reference group. The data will be log-transformed. A contrast matrix will be defined for extracted the comparison of interest such as group difference at baseline or at Week 16. The fold-changes will be derived, and volcano-plots will be provided as appropriate. The intersection between biomarker differentially expressed at baseline between lesional vs. non-lesional, lesional vs healthy skin and non-lesional vs. healthy skin will be represented graphically using Venn diagrams. The proportion of biomarker changing significantly from baseline to Week 16 will be derived for each study group. The direction of the changes will be highlighted.

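### The biomarker SAP lets missing values be filled with one mean pooled over all skin groups and visits, which would bias the group and time contrasts those data are meant to estimate

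*SAP*

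**What the plan says.** Section 2.1.2.1 of the biomarker SAP treats two kinds of gap. Values below the LLOQ have detailed rules with cut-offs at 25% and 50%. All other missing values get one sentence: "Missing values not due to measurements being below LLOQ maybe be imputed by the mean value computed across all samples, as appropriate". No condition says when this is appropriate. There is no restriction to a skin group or visit, no limit on the missing share and no sensitivity analysis.

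The same section names groups when it means groups: for LLOQ, "the number of values below LLOQ will be computed by group (lesional, non-lesional and healthy skin"). The mean over all samples therefore reads as a pooled mean.

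Section 2.5.1 sets the purpose: "The biomarker potentially linked to the disease status (lesional, non-lesion or healthy skin) and the biomarker changing with the treatment will be identified". It uses a linear mixed model "with group, visit and interaction between group and visit considered as fixed effects and subject as random effect", adds that "The data will be log-transformed", and draws contrasts such as the group difference at baseline or Week 16. Section 1.2 samples at baseline and at "Week 2, Week 4, Week 8, Week 12, EoT at Week 16, and Follow-ups at Week 22 and Week 28".

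**The concern.** A pooled mean sits somewhere between inflamed, clinically uninvolved and healthy skin, and between untreated, treated and post-treatment visits. Putting that value into a missing lesional baseline cell or a missing healthy Week 16 cell moves both towards the same centre. The quantities at stake are the ones the section 2.5.1 model is built to deliver: fold-changes between skin groups, and the share and direction of biomarkers that change by Week 16.

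The fill is also unnecessary there. A linear mixed model can be fitted to whatever values were observed, and so can the linear models of sections 2.4.1 and 2.5.3. Only the matrix methods (principal components, clustering, elastic net) need complete data.

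**Working it through.** **The plan's own figure.** The imputation rule has no figure attached. The nearest one is the planned dropout in section 1.3 of the clinical SAP: "Allowing for drop-out rate of 15%, a total of approximately 24 pediatric patients with moderate-to-severe AD will be enrolled to achieve 20 evaluable patients". Check: 20 / (1 − 0.15) = 23.5, rounded up to 24, so it reproduces. Dropout is not a biomarker missing rate. It only shows that a share such as 15% is not far-fetched if a missed visit counts as a missing value.

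**Assumptions.** The documents give no biomarker missing rate, group means or spread. Missing shares of 5% to 25% and all means below are assumed for illustration. Values are missing completely at random within each group and visit.

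**Formula.** Let cell i (a group at a visit) have true mean μᵢ and missing share mᵢ, with equal planned numbers per cell.
- Pooled mean of observed values: G = Σ(1 − mᵢ)μᵢ / Σ(1 − mᵢ).
- Expected cell mean after the fill: (1 − mᵢ)μᵢ + mᵢG.
- If every mᵢ = m, the G terms cancel in any difference, which becomes (1 − m)(μᵢ − μⱼ).

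**Equal missingness.** Differences keep 95%, 90%, 85% and 75% of their size at 5%, 10%, 15% and 25% missing. A true lesional change of −1.00 becomes −0.85 at 15%.

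**Simulation.** 20 per group, means 1.5 / 0.7 / 0 for lesional, non-lesional and healthy skin, SD 1, true lesional-minus-healthy difference 1.50:

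| Missing | Formula | Simulated after pooled fill | 95% interval coverage |
|---|---|---|---|
| 5% | 1.425 | 1.42 | – |
| 10% | 1.35 | 1.35 | about 92% |
| 20% | 1.20 | 1.19 | about 81% |

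Observed values alone give 1.50 with about 95% coverage.

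**Log scale.** The mean was taken on the raw scale and the analysis done on logs (log means 1 / 0.5 / 0, log SD 0.5, 5,000 runs, true difference 1.00). The estimate is 0.95, 0.85 and 0.74 at 5%, 15% and 25% missing. With observed values only it is 1.00 throughout.

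**Unequal missingness.**
- *No true change.* Means are 2 / 1 / 0 at both baseline and Week 16, with 15% missing only at Week 16 in the two patient skin groups. G = (2 + 1.70 + 1 + 0.85 + 0 + 0) / (1 + 0.85 + 1 + 0.85 + 1 + 1) = 5.55 / 5.70 = 0.974. The lesional Week 16 mean becomes 0.85 × 2 + 0.15 × 0.974 = 1.846, a false change of −0.15.
- *Enlarged difference.* Means are 2 / 0.5 / 0, with 15% missing in non-lesional skin only. G = (2 + 0.425 + 0) / 2.85 = 0.851. The non-lesional mean becomes 0.425 + 0.128 = 0.553, so its difference from healthy skin rises from 0.50 to 0.55.

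**Standard error.** At 10% missing in the first simulation, the average reported standard error after the fill is 0.306 and the actual spread of the estimates is 0.308. They agree. For paired change (20 children, true change −1, fill value 0.6, 10% missing at each visit, within-child correlation 0.85), the reported standard error after the fill is 0.154, against 0.134 from complete pairs. So it can also rise.

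**The case against.** **The rule is optional.** The SAP does not require the fill, and it does not say that filled values enter the mixed model. Fitting section 2.5.1 to observed values and filling only for principal components would already comply. This stands, so the finding is about a poor permitted option with no condition on its use. A reader might infer that the plan commits to this fill throughout. The text does not say so.

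**The missing share may be small.** LLOQ gaps have their own rules, and the SAP does not say whether a missed visit or only a failed assay counts as missing. At 2% missing the 1.50 difference would read 1.47. This also stands: the size depends on an unknown rate.

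**Standard errors.** A reader might infer that single imputation makes the standard errors too small. The check above does not support this: the reported value matches the true spread in the group comparison, and for paired change it can exceed the complete-pair value. The loss of coverage comes from bias.

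**Direction.** A reader might infer that the bias always runs towards no difference. That holds when missing shares are similar. Unequal shares can create or enlarge an effect.

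**Reach.** Differential testing of transcripts uses raw counts (section 2.1.1.3), section 2.6 calls all analyses exploratory, and the primary TEWL endpoint is analysed under the clinical SAP. These points limit the severity. They do not remove the bias, which sits in the estimates whether or not anything is tested.

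**Conclusion.** The point holds as a defect in a permitted method. If the pooled mean is used before the group-by-visit model, group differences and change to Week 16 are biased. With similar missing shares the loss equals the share: about 5% to 20% of the difference over an assumed 5% to 20% missing. In the simulated example, coverage is about 92% at 10% missing and 81% at 20%. The coverage figures depend on the assumed 1.5 SD difference and 20 per group; the (1 − m) factor does not. With unequal shares a false change can appear. The effect falls mainly on lipidomics, proteomics and filaggrin breakdown products. It does not touch the primary endpoint, and it is negligible if very few values are missing. It should be changed because a better method is available at almost no cost.

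**What to change.** - Delete the pooled-mean option from section 2.1.2.1 of the biomarker SAP.
- Fit the mixed model of section 2.5.1 and the linear models of sections 2.4.1 and 2.5.3 to observed values. State the missing-at-random assumption this rests on.
- State whether a missed visit, or only a failed measurement in a collected sample, counts as a missing value.
- Where a complete matrix is needed for description (principal components, clustering), impute within skin group and visit or by nearest neighbours. Report the share imputed and add a complete-case check.
- For the elastic-net and random-forest classifiers (sections 2.5.2 and 2.5.3), impute without using the outcome label, and inside each fold wherever cross-validation is used. A fill by skin group would build the class label into the predictors and inflate the cross-validated accuracy.

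The cost is a few lines of SAP text and a little more code for the matrix methods and classifiers. No data collection changes.

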2.1.2.2 Outlier detection

Biomarker will be investigated for outliers regardless of group or visit. A value will be declared outlier if it falls out of the interval $[Q1-3*IQR, Q3+3*IQR]$, where Q1 denotes the first quartile,

Q3 the third quartile and IQR the interquartile range. Outliers will be imputed by $Q1-3*IQR$ and $Q3+3*IQR$, respectively. Samples will be investigated for possible contamination that may lead to sample being outlier. For this purpose, samples boxplots, principal component analyses (PCA) hierarchical cluster dendrogram will be used. Outlier samples will be scrutinized and maybe discarded from the statistical analyses.

The distribution of biomarkers will be assessed by histogram and QQ-plot. The values may be log-transformed to fit a Gaussian distribution prior to some statistical analyses. The standardization may be performed for multivariate analyses.

2.1.2.3 *Batch effect assessment*

Samples maybe analyzed or transferred to NJH in different batches. PCA will be computed and a visual inspection of the projection of the samples on the first principal components will enable a first view of the potential batch's effect. The batch effect will be assessed using a linear model estimating a batch effect for each biomarker. This model will include the batch effect, the visit, the health status and interaction between visit and health status. The relevance of the correction for batch effect will be assessed by the p-values of the batch effect.

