2 STATISTICAL AND ANALYTICAL PROCEDURES

2.1 PREPROCESSING AND QUALITY CONTROL

2.1.1 Data normalization

2.1.1.1 *Lipidomics*

STS samples processing for lipid extraction will be done as described in [Section 4.1.1](#). Lipidomic data will be provided as absolute concentration in pmol/mg protein or in ug/mg protein requiring no normalization step. Values below limit of quantification (LLOQ), missing values, and outliers will be treated as described in [Section 2.1.2](#).

2.1.1.2 *Proteomics*

There is no normalization step performed after sample analyses as specified by National Jewish Health (NJH). Polar metabolite samples will be normalized based on sample protein values before running the assay then signal intensities are expressed relative to healthy volunteers' group.

2.1.1.3 *Transcriptomics*

Raw sequencing data (fastq files) will be taken through successive steps to generate expression measures at gene level (counts): quality control, adapter trimming and filtering, mapping of reads to the human reference genome or pseudo-alignment to the transcriptome, quantification. These steps will be performed by NJH. The raw and the preprocessed transcriptomic data will be sent to Sanofi.

Samples filtering

Total RNA from the skin tapes will be normalized for cDNA generation and preparation of sequencing libraries. Both the cDNA and sequencing libraries generated will be quantified and qualified using the Bioanalyzer High-Sensitivity DNA chip. Samples that will yield low quality cDNA and sequencing libraries will not be sequenced.

Gene filtering

Genes having very low counts across all libraries will be filtered out. For this purpose, the count per million (cpm) values will be computed. Counts per million are counts scaled by the number of sequenced fragments in a sample (library size) times one million. Genes with less than 1 cpm in more than half of the samples will be filtered out. This filtering rule will be applied separately for count data matrices in HV and AD cohorts. Genes that successfully pass the filter in at least one data set will be kept. The specific threshold of 1 cpm may be adjusted depending on count distribution in the dataset.

Normalization and transformation of counts data

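### For lipid and protein markers raised in untreated lesions, the pooled outlier rule, read on the raw scale, replaces true baseline values and biases the fall to Week 16 towards zero

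*SAP*

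**What the plan says.** Section 2.1.2.2 of the biomarker SAP fixes three things.

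- **Reference set.** "Biomarker will be investigated for outliers regardless of group or visit", so the quartiles come from lesional, non-lesional and healthy skin at all visits together.
- **Criterion.** "A value will be declared outlier if it falls out of the interval" from Q1-3*IQR to Q3+3*IQR.
- **Action.** "Outliers will be imputed by $Q1-3*IQR$ and $Q3+3*IQR$, respectively". No review of the single value comes first. The contamination check that follows concerns whole samples. No analysis without the replacement is planned.

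The scale is left open. The next paragraph of the section says "The values may be log-transformed to fit a Gaussian distribution prior to some statistical analyses", which is permissive and comes after the rule. Section 2.5.1 does require log-transformed data, but for the mixed model, and it does not say that the fences are set after that step. Section 2.1.1.1 says "Lipidomic data will be provided as absolute concentration in pmol/mg protein or in ug/mg protein requiring no normalization step", so the lipid data arrive on the raw scale.

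The main contrasts are in section 2.5.1: group by visit, group differences at baseline and Week 16, and fold changes. It adds: "The proportion of biomarker changing significantly from baseline to Week 16 will be derived for each study group".

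**The concern.** A fence is meant to catch technical errors. Here the reference set is mostly healthy, non-lesional or treated skin, and untreated lesional skin is a small share of it. If a marker is high in active disease and falls on treatment, the fence describes normal and treated skin, and real disease values lie beyond it.

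The replacement is one-sided. For a positive, skewed marker the lower fence is usually negative, so low values are never raised. Week 16 lesional values are near the bulk of the pool and are rarely cut. The loss thus falls on the baseline lesional cell, and both contrasts that use it shrink. It is largest for the markers that respond most, which can also distort their ranking.

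The plan recognises this kind of dependence just above. In section 2.1.2.1, when 25% to 50% of values are below the LLOQ, it tests whether they cluster in one skin group. The outlier rule has no such safeguard.

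**Working it through.** **Sample counts.** The only related figure in the plan is the enrolment number: 20 evaluable with 15% drop-out (clinical SAP, 1.3) gives 20/0.85 = 23.5, rounded up to 24. This agrees with "Approximately 24 pediatric patients with moderate-to-severe AD will be enrolled to achieve 20 evaluable patients". Biomarker SAP 1.2 lists eight sampling visits: Weeks 0, 2, 4, 8, 12, 16, 22 and 28. With 20 per group, 3 x 20 x 8 = 480 samples, of which 20 are untreated lesional: 20/480 = 4.2%, or 1 in 24. (The list in 1.7.1 omits Week 28; with seven visits the share is 1 in 21.)

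**Where the fences fall.** Take a lognormal pool at healthy level with median 1 and log SD s. Then Q1 = exp(-0.674s) and Q3 = exp(0.674s).

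- s = 0.5: Q1 = 0.714, Q3 = 1.401, IQR = 0.687. Upper fence 1.401 + 3 x 0.687 = 3.46; lower fence 0.714 - 3 x 0.687 = -1.35.
- s = 0.8: Q1 = 0.583, Q3 = 1.715, IQR = 1.132. Upper fence 1.715 + 3 x 1.132 = 5.11; lower fence 0.583 - 3 x 1.132 = -2.81.

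The lower fence equals 4 x Q1 - 3 x Q3, so it is negative whenever Q3/Q1 exceeds 4/3. On the log scale the upper fence is (0.674 + 3 x 1.349) x s = 4.72s, that is 10.6 times the median at s = 0.5 and about 44 times at s = 0.8. In the real pool, non-lesional and partly treated samples raise the raw fence somewhat, so simulation is needed.

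**Simulation on the raw scale, pooled fences.** 480 samples, 400 runs per setting, lognormal marker, within-subject correlation 0.5. All marker inputs are assumptions; the documents give none. The lesional log excess at the eight visits, as a fraction of its baseline value, was:

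- fast path: 1, 0.7, 0.45, 0.25, 0.2, 0.2, 0.2, 0.25; non-lesional 0.2 throughout;
- slow path: 1, 0.9, 0.8, 0.65, 0.55, 0.5, 0.6, 0.7; non-lesional half of lesional at each visit.

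Loss = 1 - (log2 change to Week 16 after replacement / before). Entries are for log SD 0.5 / 0.8.

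| Baseline excess | Fast: replaced | Fast: loss | Slow: replaced | Slow: loss |
|---|---|---|---|---|
| 2-fold | 8% / 8% | 3% / 5% | 4% / 6% | 2% / 3% |
| 4-fold | 33% / 24% | 10% / 9% | 13% / 14% | 4% / 7% |
| 8-fold | 73% / 49% | 23% / 17% | 25% / 24% | 7% / 10% |

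For example, at 8-fold on the fast path the log2 change goes from -2.42 to -1.87 (1 - 1.87/2.42 = 23%) and from -2.39 to -1.98 (17%). About 1% or less of healthy values and about 2% or less of Week 16 lesional values are replaced.

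**Baseline lesional-healthy gap.** A separate set of runs used log SD 0.4 / 0.7, lesional log excess falling to 20% by Week 16, and non-lesional excess at 35% of lesional. The log gap is cut by 2% / 3% at 2-fold and 5% / 5% at 3-fold. At 10-fold the estimated ratio drops from 10.1 to 6.0 / 7.0.

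**Same rule under other conditions.**

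- Pooled fences on the log scale: at most about 1% of baseline lesional values replaced at 8-fold, and at most 2.5% at 20- to 50-fold; attenuation about 0-1%.
- Raw fences within group and visit: about 1-2% replaced, no log-scale attenuation.
- Markers reduced in lesions (ratio 0.5 to 0.1, raw scale): lesional values essentially untouched; at 0.1 and log SD 0.7 the ratio moves from 0.101 to 0.102.

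**The case against.** The strongest reply is that the plan does log-transform. Section 2.5.1 makes it mandatory for the model that gives the fold changes, and section 2.2.2 uses log data for the principal component plot. If the fences were set after that step, the harm would almost disappear. The core defect is then an unfixed order of steps rather than pooling as such. Much of this stands, and it shapes the fix. It does not clear the text, because the replacement is described as preprocessing, before an optional log step, so a programmer following it would work on the raw scale.

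Further limits also stand.

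- Section 4.1.1.2 expects EOS CER to be low and NS CER high in AD skin, so the EOS-to-NS ratio named in 1.3.3 is expected to be low in lesions and outside the problem.
- Section 2.1.1.3 runs DESeq on raw counts for differential testing and uses a transformation that includes log2 for other analyses, so transcriptomics is not clearly reached.
- The large losses need 8-fold excess or more and fast normalisation. Another slow path gave 21-23% replaced and 5-10% loss at 8-fold, so the lower ends above are not bounds.
- Section 2.6 makes all biomarker analyses exploratory, and bias towards zero would not create a false treatment signal. But waiving formal tests does not excuse a rule that biases the estimates.

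A reader might infer that the rule shrinks the dupilumab effect on biomarkers in general, or touches the trial's efficacy result. The documents support neither. The effect is confined to markers high in lesions under raw-scale fences, and the TEWL endpoints do not pass through this rule.

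**Conclusion.** The rule is wrong as written, in a conditional way. On the raw scale, for lipid and protein markers raised in untreated lesions and falling on treatment, pooled fences with automatic replacement bias the baseline excess and the fall to Week 16 towards zero. The loss in log2 change is small at a 2-fold excess, moderate at 4-fold, and up to about a quarter at 8-fold when skin normalises quickly. At that extreme most of the baseline lesional cell is declared outlying, which is no longer outlier detection. The direction rests on the text and the sampling scheme. The size rests wholly on the assumed fold excess, log SD and time course, for which the documents give no figures.

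**What to change.** In biomarker SAP 2.1.2.2:

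1. State that fences are computed on log-transformed values, preferably on residuals from the group-by-visit model of 2.5.1, otherwise pooled on the log scale.
2. Use the fences to flag values for a technical check, and do not replace values automatically.
3. Report the mixed-model results with and without handling of flagged values.
4. Say how values imputed below the LLOQ under 2.1.2.1 are treated. Draws close to zero can lie far out in the lower log tail and be flagged for that reason alone.

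The cost is one paragraph and slight programming work. The downside is that an occasional extreme value without a technical explanation stays in the main analysis; the second set of results shows how much it matters.

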1 OVERVIEW AND INVESTIGATIONAL PLAN

1.1 INTRODUCTION

Atopic dermatitis (AD) is a chronic systemic inflammatory skin disease with a prevalence of up to 25% in children and up to 7% in adults. AD is caused by the complex interplay between epithelial dysfunction and dysregulated/over-activated Type 2 immune response in the skin, with a special role for IL-4/IL-13-driven signaling in AD pathogenesis. This Type 2 hyperactivation blocks terminal differentiation of skin keratinocytes and formation of a mature stratum corneum that is mainly responsible for the skin barrier function.

Dupilumab is a human monoclonal antibody that blocks the shared receptor subunit for interleukin (IL) -4 and IL-13, thus inhibiting signaling of both IL-4 and IL-13, cytokines that are key drivers of Type 2 inflammatory diseases. Dupilumab is recently approved in the US for the treatment of pediatric patients ≥ 6 and < 12 years of age with moderate-to-severe AD whose disease is not adequately controlled with topical prescription therapies or when those therapies are not advisable.

The LPS16764 study is an open label exploratory phase 4 study designed for assessing the effect of subcutaneous injection of dupilumab on skin barrier function measured as transepidermal water loss (TEWL) in AD pediatric patients. The effect of dupilumab treatment on skin barrier function is evaluated using TEWL in conjugation with skin lipidomics, proteomics, and transcriptomics generated from skin tape stripping (STS) samples. Skin barrier structure changes is evaluated using optical coherence tomography (OCT) and Fourier-Transform Infrared (FTIR) spectroscopy in both predefined lesional and non-lesional skin areas.

This document provides a statistical analysis plan for all biomarker data repeatedly collected during the LPS16764 study. The term biomarker in this document will then refer to lipidomics, proteomics, transcriptomics, or filaggrin (FLG) breakdown products. TEWL may refer to a measurement before STS; after a given number of STS samplings or can be AUC (area under the curve) of TEWL before STS and after STSs performed at the specified STS visits. The term study group or group in general refers to lesional, non-lesional or normal health skin group. This biomarker statistical analysis plan is based on clinical trial protocol Version 1 (13-Jul-2020).

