Normalization is a process designed to remove systematic technical differences between samples to ensure that technical bias has minimal impact on the results. One can envisage within-sample and between-samples normalization. In this study since we are interested in differential expression between experimental conditions rather than comparing expression of different genes in a sample, only a between-sample normalization will be performed. Using the DESeq2 R package, variance stabilizing transformation (VST) will be applied for analyses other than differential testing, for example clustering of samples or other machine learning applications. For differential testing the DESeq function will be applied to raw counts.

Included in VST, a log2 transformation is performed after addition of a small offset to avoid taking the log of zero. The quality of the normalization will be assessed by plotting the densities of variance-stabilized counts for the different samples. Since it is assumed that most of the genes are unaffected by the experimental conditions, a successful normalization should lead to overlapping densities. The mean-variance association will also be investigated before and after normalization. Samples boxplots will be plotted before and after normalization.

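### The biomarker batch check ignores that samples are repeated within a child, its p-value decides on correction, and the main biomarker model has no batch term to catch what is missed

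*SAP*

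**What the plan says.** All references are to the biomarker SAP.

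- **Section 2.1.2.3, whether batches occur.** The plan allows for them without describing them: "Samples maybe analyzed or transferred to NJH in different batches". After a visual look at principal components, "The batch effect will be assessed using a linear model estimating a batch effect for each biomarker".
- **Section 2.1.2.3, the model.** "This model will include the batch effect, the visit, the health status and interaction between visit and health status". No subject term is listed.
- **Section 2.1.2.3, the decision.** "The relevance of the correction for batch effect will be assessed by the p-values of the batch effect". No cut-off, multiplicity rule or correction method is given.
- **Section 2.5.1, the main differential model.** It is specified "with group, visit and interaction between group and visit considered as fixed effects and subject as random effect". Batch is not in it.
- **Section 2.1.1.3, transcriptomics.** "For differential testing the DESeq function will be applied to raw counts".
- **Section 2.4.3.** Repeated values of a biomarker are modelled with a random subject effect, and the intra-class correlation (ICC) is to be estimated.

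**The concern.** Sections 2.4.3 and 2.5.1 treat samples from one child as correlated. The batch check in 2.1.2.3 treats them as independent, so its p-value does not have its nominal meaning. There are two possible errors, and they belong to different layouts:

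- **A child's samples share a batch.** Ordinary differences between children then look like batch differences, and the test flags batch too often.
- **Batches cut across children.** Between-child variation sits in the residual, and the test misses real batch shifts that a model with the child in it would find.

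Neither error is repaired later. A missed shift enters the 2.5.1 model, which has no term to absorb it. For transcriptomics, values corrected beforehand do not reach the differential test at all, because that test starts from raw counts. At stake are the biomarker contrasts between patients and volunteers and, where batches cut across children, contrasts over time as well.

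**Working it through.** **Inputs from the documents**
- 20 evaluable patients and 20 evaluable volunteers (section 1.2 of the biomarker SAP). The enrolment figure reproduces: 20 / 0.85 = 23.5, rounded up to 24, using the 15% drop-out in clinical SAP section 1.3.
- Eight sampling visits: Weeks 0, 2, 4, 8, 12, 16, 22 and 28 (section 1.2). One sentence of 1.7.1 stops at Week 22, but the list below it has tape stripping at Week 28, so eight are used.
- Two skin areas per patient and one per volunteer, so 20 x 2 x 8 + 20 x 8 = 320 + 160 = 480 samples.

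**Assumptions, because the plan is silent**
- Two-sided 5% cut-off, 2 to 5 batches, ICC 0.1 to 0.7, within-group variance 1.
- Lesional skin shifted by 0 or 1 SD.
- Health status read as two levels (patient or volunteer) or three (skin groups).

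**Layout A: each child's samples in one batch, no true batch effect**

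The variance of a batch difference is inflated by about 1 + (m - 1) x ICC, where m is the sample-weighted number of samples per child: m = (320 x 16 + 160 x 8) / 480 = 13.3. The approximate false-flag rate with B batches is P(chi-square on B - 1 df > critical value / inflation).

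| ICC | Inflation | 2 batches | 3 batches | 5 batches |
|---|---|---|---|---|
| 0.1 | 2.23 | 19% | 26% | 37% |
| 0.3 | 4.70 | 37% | 53% | 73% |
| 0.5 | 7.17 | 46% | 66% | 86% |

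Simulation of the listed model (1,000 to 2,000 runs per setting, ranges over repeated runs and both readings of health status) agrees:
- 2 batches: 15-18% at ICC 0.1, 30-35% at 0.3, 43-48% at 0.5.
- 3 batches: 26% to 67% over ICC 0.1 to 0.5.
- 5 batches: 39% to 86% over the same range.

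A test on child means, which respects the child, returns to 4-6%.

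**What a false flag costs in layout A.** Centring on batch removes on average (B - 1) / (40 - 2) of the between-child variance: 1/38 = 2.6% for 2 batches and 3/38 = 7.9% for 4. An additive correction shifts all of a child's values equally, so changes from baseline and lesional versus non-lesional differences within a child cancel it. Only patient-versus-volunteer contrasts are touched.

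**Layout B: two batches cutting across children**

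- *No true shift:* false flags in about 5% under the listed model.
- *True shift of 0.2 SD, listed model:* standard error 2 / sqrt(480) = 0.091, z = 0.2 / 0.091 = 2.19, power = Phi(2.19 - 1.96) = 59%. Simulation gives 50-59%; the lower end arises when lesional skin differs by 1 SD and health status has two levels.
- *Same shift, child in the model:* the residual SD falls to sqrt(1 - ICC), so the standard error is about 0.091 x sqrt(1 - ICC). For ICC 0.3, 0.5 and 0.7 this gives at most 74%, 87% and 98%. Simulation with child effects fitted, which costs degrees of freedom, gives 68-70%, 82-84% and 96%.

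So 41-50% of such shifts would be missed under the plan's check, against 4-32% with the child in the model.

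**The case against.** Much of the opposing case narrows the point, and these parts stand:

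- **The high false-flag rates belong to one layout.** The plan says only that batches may occur. If they cut across children, the rate is nominal. The two errors should not be added together.
- **The loss per false flag is small**, and within-child contrasts survive it.
- **Adjusting every biomarker absorbs the same chance differences in all of them.** True for a fixed batch term, so the remedy has a real if small price. The difference is that a term in the model carries its uncertainty into the intervals and treats all biomarkers alike.
- **Lipid and protein data might be corrected before modelling**, since batch sits under preprocessing. The plan does not say so, and this route is closed for DESeq on raw counts.
- **The work is exploratory** (section 2.6). That limits the claims made from it, but does not make an invalid p-value a sound basis for preprocessing.

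A reader might also infer three stronger things that the text does not support:

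- *Correction is decided biomarker by biomarker, leaving a mixture in one volcano plot.* The model is fitted per biomarker, but the sentence speaks of one correction and several p-values. One decision for a whole dataset is an equally natural reading.
- *The check omits skin area.* The plan's usual name for the three-level factor is group ("The term study group or group in general refers to lesional, non-lesional or normal health skin group"), but health status is undefined and close to "disease status (lesional, non-lesion or healthy skin" in 2.5.1. The result does not depend on it.
- *Batches follow sites and so remove severity differences.* Nothing in the documents says how batches relate to sites, and volunteers are matched to patients on site.

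**Conclusion.** The point holds in a limited form. Whenever samples are run in more than one batch, the p-value in 2.1.2.3 is a poor basis for deciding on correction: too liberal if batches follow children, too weak if they cut across them. The main model does not make good a missed effect. The sizes shown rest on an assumed 5% cut-off, assumed ICCs, numbers of batches and shift size, and one of two layouts; the plan states none of these. If there is only one batch, the issue does not arise. Severity is minor to moderate: the analyses are exploratory, no TEWL endpoint is affected, and the loss from a false correction is small. The more consequential part is a real batch shift left in the group contrasts.

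**What to change.** - Do not use this p-value to decide on correction.
- When samples were run in more than one batch, include batch in the 2.5.1 mixed model for all biomarkers, keeping the random subject and the three-level skin group. Include it in the DESeq design as well.
- Use a random subject effect in any batch test that is kept. Fixed child effects would not do, because batch cannot be estimated alongside them when all of a child's samples share a batch.
- Define health status in 2.1.2.3 as the three-level skin group.
- Keep the principal component plot as a check.
- Tabulate batch by skin group and site, and state where batch and group cannot be separated.

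The cost is some wording and one model term. If there is no true batch effect, between-child contrasts become slightly less precise: with 2 to 4 batches as fixed effects that follow children, 1 to 3 of 38 between-child degrees of freedom are spent.
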